Tumor sample for pathology confirmation ¹	×																4
Plasma PK ^J		* ×		×	* ×		×		×		***************************************						6.6.1.2
Whole blood for ex vivo pSTATs ^K		*		×													6.7.1
Blood sample for pharmacogenetics research (optional) ^L	×																6.7.1
CT Scan (with contrast unless contraindicated) M	×					×			×			X, then cycles	X, then every 3 cycles				6.9.1
$ m PET^N$	×					×											6.9.2
Bone marrow aspiration and biopsy ⁰	×				***************************************	.,,,,,,,,,,,,,,,,,,,,,,,,,,,,,,,,,,,,,,				•	••••••						6.9.1
AZD4205 administration ^P		×	li .	li .	11	11	11	11	11	11	II		×				8
Survival																×	6.9.5

Footnote for Schedule of Study Activities (Part B):

- * Multiple time points. Details can be found in corresponding sections.
- A. Screening tests should be performed within 28 days before the first administration of study drug.
 - 3. A safety follow up visit will occur 28 days (± 7) from the last dose of study drug.
- 3 months for survival information, for collection of details of subsequent treatment regimens received following withdrawal from study drug In the Phase 2 expansion, following disease progression, the patient, patient's family, or the patient's current physician must be contacted every and to follow up unresolved AEs (unless the patient withdraws consent) regardless of date of last contact.
 - D. Both HBsAg and HBcAb should be negative for eligibility.
- PFTs (including spirometry and DLCO) will be performed at screening, Cycle 3 Day 1 and then every 6 weeks and whenever clinically indicated. щ
 - AEs will be collected and recorded in CRF from first dosing of AZD4205 until the end of the follow up period (28 ±7 days post lase dose). However, SAE should be recorded in CRF from ICF signing to the end of defined follow-up period. ŗĽ,
- Echocardiogram or MUGA scan to assess LVEF will be conducted at screening (prior to first dose of AZD4205), Cycle 3 Day 1, then every 12 weeks for the rest of cycle. J.
 - In the Phase 2 expansion, laboratory tests for screening should be performed within 7 days prior to the planned first dosing date. In addition, laboratory tests do not need to be repeated at baseline if the baseline visit is within 3 days of the screening sample. H.

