6.4.6 Safety follow-up

An end of study treatment assessment will be performed at the time investigational product is permanently discontinued (see Table 2 and Table 3).

In addition, a 28-day follow-up should be made by telephone contact after 28 days (± 7 days) following the discontinuation of the study treatment to collect new AEs and follow up on any ongoing AEs and concomitant medications (including any subsequent cancer therapy). Refer to section 6.5.3 for full details on AE recordings during follow-up.

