6.5.3 Recording of adverse events

Time period for collection of adverse events

AEs will be collected and recorded in eCRF from first dosing of AZD4205 until the end of the follow up period. The follow-up period is defined as 28 days (± 7 days) after study treatment is discontinued. However, SAE should be collected and recorded in eCRF from ICF signing to the end of defined follow-up period (see Table 5).

Table 5 Summary of recording and follow-up of adverse events

	Consent to Randomization/first dosing	Until defined Follow up Visit (safety follow-up period)	Post Follow-up visit but prior to progression (if applicable)
Record all new AEs in CRF	No*	Yes	No
Record all ongoing AEs in CRF	No	Yes	No**
Record all study procedure related new SAEs in CRF	Yes	Yes	No***

^{*} Adverse events prior to the first dosing but worsening post the first doing should be recorded in eCRF as new AEs.

** All ongoing AEs/SAEs post safety follow-up period will be followed by investigator as long as medically indicated, but without further collection in eCRF.

After the final database lock, there may be some patients remaining on study treatment. For these patients who are continuing to receive AZD4205, Sponsor will collect information (during the treatment period and for 28 +/- 7 days after last dose) on SAEs, deaths (including those due to disease progression), discontinuation due to AEs/SAEs and drug accountability only.

^{***} New emerging SAEs post follow-up period including death should not be collected in eCRF, but still need to be reported to Dizal in the condition of causality with study procedure judged by investigator.

Follow-up of unresolved adverse events

Sponsor retains the right to request additional information for any patient with ongoing AE(s) at the end of the study, if judged necessary.

If an investigator learns of any SAEs, including death, at any time after a patient has completed the study and he/she considers there is a reasonable possibility that the event is related to AZD4205, the investigator should notify Sponsor.

Variables

The following variables will be collected for each AE:

- AE diagnosis/description
- The date when the AE started, stopped and intensity changed
- CTCAE grade (version 5.0); for the grading of specific ocular AEs, refer to Appendix VII (Table 18)
- Whether the AE is serious or not
- Investigator causality rating against the investigational product (yes or no)
- Action taken with regard to investigational product
- Outcome

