Any AE occurring within the defined 28 days follow-up period after discontinuation of investigational product will be included in the AE summaries. Any adverse events in this period that occur after a patient has received further therapy for cancer (following discontinuation of investigational product) will be flagged in the data listings.

Hematology, clinical chemistry, vital signs, ECG data, Echo/MUGA data and pulmonary function test data will be listed individually by patient and suitably summarized. For all laboratory variables, vital signs and ECG data, which are included in the current version of CTCAE, the CTCAE grade will be calculated. Summary statistics of mean, median, standard deviation, minimum, maximum and number of observations will be used.

Details of any deaths will be listed for all patients.

Any qualitative assessments will be summarized for all patients using the number and proportion of patients with results of negative, trace or positive.

Graphical presentations of safety data will be presented as is deemed appropriate. This may include, but is not restricted to, presentation of parameters against time, concentration or shift plots. Appropriate scatter plots will also be considered to investigate trends in parameters compared to baseline.

Pharmacokinetics

This will be summarized in the PK analysis set.

Plasma concentrations of AZD4205 will be summarized by nominal sample time. Plasma concentrations and derived PK parameters will be summarized by dose cohort. Parameters following single and multiple dosing will be summarized separately. Plasma concentrations at each time point will be summarized according to dose cohort by the following summary statistics:

- The geometric mean (G_{mean} , calculated as $exp[\mu]$, where μ is the mean of the data on a logarithmic scale)
- Coefficient of variation (CV, calculated as $100\sqrt{[\exp(s2)-1]}$, where s is the standard deviation of the data on a log scale)
- $G_{mean} \pm standard deviation (calculated as exp[<math>\mu \pm s$])
- Arithmetic mean calculated using untransformed data
- Standard Deviation calculated using untransformed data
- Minimum
- Maximum
- Number of observations

The following summary statistics will be presented for $AUC_{(0-24)}$, $AUC_{(0-t)}$, AUC_{ss} , C_{max} , $C_{ss\ max}$ and $C_{ss\ min}$:

- G_{mean} , calculated as $\exp[\mu]$, where μ is the mean of the data on a logarithmic scale)

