4.3.2 Adverse Events (AE)

All AEs recorded on the CRF will be coded using the Medical Dictionary for Regulatory Activities (MedDRA) dictionary Version 22.0 (or a later version if updated during the study).

Statistical Analysis Plan of PTCL (Version 3.0)

Protocol Code: DZ2019J0005 (Part B)

Date: Mar 25, 2023

The AEs will be classified as pre-treat AEs or treatment-emergent AEs (TEAEs), as below:

- Pre-treat AEs are events that start prior to the date of the first dose of investigational product.
- TEAEs are events with start or worsen on or after the date of first dose of treatment and up to 28 days after last dose of treatment or the day prior to the subsequent anti-cancer therapy initiation after treatment discontinuation (including participation in a new clinical trial), whichever is earlier.

Assessment of AE grade will be based on the National Cancer Institute-Common Terminology Criteria for Adverse Events (NCI-CTCAE, version 5.0).

A treatment-related AE is an AE considered by the investigator as ‘related’ or with unknown/missing relationship to treatment.

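### New-AE recording can close on day 21 after treatment while the SAP counts TEAEs to day 28 after last dose, so TEAE counts depend on when the site calls

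*Protocol*

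**What the plan says.** **Collection.** Protocol 6.5.3 sets the span: "AEs will be collected and recorded in eCRF from first dosing of AZD4205 until the end of the follow up period". It then defines that end point: "The follow-up period is defined as 28 days (± 7 days) after study treatment is discontinued". Table 5 answers Yes for new AEs up to the follow-up visit and No after it. Section 6.9.5.1 adds that only later cancer therapy and response assessments are collected beyond that visit. The visit is a single telephone call; 6.4.6 says "a 28-day follow-up should be made by telephone contact after 28 days", with the same tolerance of 7 days either way.

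**Analysis.** SAP 4.3.2 takes AEs recorded on the CRF and counts as treatment-emergent those starting or worsening "up to 28 days after last dose of treatment", or up to the day before new anti-cancer therapy if that is earlier. SAP 5.7.1 puts only TEAEs in the summary tables. SAP 7.1 uses the same 28-day limit for worst-case safety summaries. Protocol 7.7 also gives 28 days without a tolerance: "Any AE occurring within the defined 28 days follow-up period after discontinuation of investigational product will be included in the AE summaries".

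**Starting date.** The Table 3 footnote counts from last dose: "A safety follow up visit will occur 28 days (± 7) from the last dose of study drug". Sections 3.1.3 and 5.3.1, the Table 2 footnotes and the SAP do the same. Section 6.4.6 instead times the call "following the discontinuation of the study treatment to collect new AEs and follow up on any ongoing AEs"; 6.5.3, 6.9.5 and 7.7 also count from discontinuation.

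**The concern.** The end of data collection floats between day 21 and day 35, while the end of the analysis window is fixed at day 28. When the contact comes before day 28, the last days of the window have no recorded data behind them, yet the patient stays in the TEAE denominators. Two sites that both follow the protocol can therefore report different TEAE counts for the same clinical course.

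Part B is meant to support a marketing application, and AEs are a stated secondary outcome. Protocol 5.2.3 lists thrombocytopenia, neutropenia and pneumonia as the commonest drug-related events of grade 3 or higher, and Appendix VII reports opportunistic infections. Events of this kind may appear in the weeks after stopping, so the tail of the window deserves consistent ascertainment.

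The two starting dates add a second inconsistency. They coincide for a patient who stops abruptly, but not for one whose treatment is interrupted for toxicity and only later declared discontinued.

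**Working it through.** The plan states no figure for this point, so there is none to reproduce. The check is window arithmetic.

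**Inputs**
- Contact: 28 ± 7 days (Protocol 6.4.6, 6.5.3, footnotes to Tables 2 and 3; SAP Appendix A).
- Event that closes new-AE recording: the follow-up visit (Protocol Table 5, 6.9.5.1).
- TEAE window: to day 28 after last dose, or the day before new anti-cancer therapy if earlier (SAP 4.3.2).
- Maximum interruption before non-recovery requires permanent discontinuation: 14 or 21 days (Protocol Table 1 and the text after it).

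**Step 1: the gap, counting from last dose.** Earliest close = 28 − 7 = day 21; latest = 28 + 7 = day 35. For a contact on day *c*, unrecorded days = max(0, 28 − *c*). At *c* = 21 this is 7 days (days 22 to 28), or 7/28 = 25% of that patient's post-treatment days. At *c* ≥ 28 it is 0. At *c* = 35, 7 extra days are collected that the SAP does not count.

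**Step 2: who loses nothing.** If new anti-cancer therapy starts by day 22, the TEAE window has closed by day 21, and even the earliest contact covers it.

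**Step 3: illustrative size.** The documents give no distribution of call days or of AE onset, so these are assumptions.
- Calls uniform over the 15 days from 21 to 35: 7/15 = 47% come before day 28, and the mean shortfall is (7+6+5+4+3+2+1)/15 = 28/15 = 1.9 days per patient.
- Share of post-treatment in-window onsets falling in days 22 to 28, if onset declines at rate *r* per day: (e^(−21*r*) − e^(−28*r*)) / (1 − e^(−28*r*)). A constant rate gives 25%; *r* = 0.02 gives 20%; 0.05 gives 14%; 0.10 gives 7%. This applies only to a patient called on day 21.
- Against the whole TEAE window, which starts at first dose: with two 21-day cycles on treatment, 7/(42 + 28) = 10% of that patient's days; with about six months, about 3%.

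**Step 4: the two anchors.** If discontinuation is declared *d* days after last dose, the discontinuation anchor puts the contact on days *d* + 21 to *d* + 35 after last dose. The Table 1 cases assume dosing stopped at onset of the toxicity.

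| Days from last dose to discontinuation | Contact, last-dose anchor | Contact, discontinuation anchor |
|---|---|---|
| 0 | 21 to 35 | 21 to 35 |
| 14 | 21 to 35 | 35 to 49 |
| 21 | 21 to 35 | 42 to 56 |

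Under the discontinuation anchor the largest gap is max(0, 7 − *d*), so it disappears once *d* reaches 7. Under the last-dose anchor it stays at up to 7 days. With *d* = 21, the earliest last-dose contact falls on the day discontinuation is declared; with *d* = 14 it falls 7 days later.

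**Step 5: does another passage close the gap?** No passage requires a second call or keeps new-AE recording open after an early one. The three-monthly survival contact (Table 3, footnote C) covers unresolved AEs, not new ones. SAP Appendix A repeats the 28 ± 7 day collection period, so the mismatch also sits inside the SAP and does not arise merely because the SAP was written against an earlier protocol version.

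**The case against.** The best counter-reading is that the 7 days are only a visit window around a fixed 28-day period, as 7.7 suggests. On that reading there is wording to clarify and no real gap. It does not displace the text: 6.5.3 attaches the tolerance to the period itself and Table 5 closes recording at the visit, so a site that follows them may stop at day 21.

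Other limits stand in full:
- A reader might infer that a quarter of AEs are lost. The documents do not support that. The 25% is a share of one patient's post-treatment days, given a call on day 21.
- A reader might infer that late serious toxicity goes unseen. It does not. Section 6.5.3 still has investigators notify the sponsor of SAEs thought related to AZD4205 and report those linked to study procedures, and survival follow-up captures deaths. What is missing is the eCRF record that feeds the TEAE tables.
- A reader might infer that unobserved days enter a rate as event-free time. SAP 5.7.1 specifies participant counts and percentages, not person-time rates. A missed event changes a table only if it would have been the patient's first in that category or would have raised the maximum grade.
- A reader might infer that patients stopped after an interruption lose most. Under the discontinuation anchor those interrupted for at least 7 days lose nothing; only the last-dose anchor leaves them exposed.
- Last dose is the commoner usage, and discontinuation may be loose wording for the same date. That is a reason to reconcile the passages.

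**Conclusion.** The point holds as a mismatch between collection and analysis. For a patient contacted before day 28 who has not started new anti-cancer therapy, up to 7 days of the TEAE window go unrecorded in the eCRF. The effect on TEAE counts is downward only and varies with call date. Its size in this trial cannot be estimated, because neither the share of early calls nor the timing of late AEs is given; the percentages above rest on the stated assumptions. The two anchors are a separate, real inconsistency of up to 14 or 21 days for patients discontinued after a Table 1 interruption. Safety in Part B is a descriptive secondary objective and the primary ORR analysis is not touched, so this is an inexpensive correction worth making and not a threat to the trial's main conclusion.

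**What to change.** 1. Schedule the contact no earlier than day 28 after last dose: 28 days, +7, with no minus. This applies to Protocol 3.1.3, 5.3.1, 6.4.6, 6.5.3, 6.9.5, the footnotes to Tables 2 and 3, and SAP Appendix A.
2. State in 6.5.3 and Table 5 that AEs with onset through at least day 28 after last dose are recorded in the eCRF whatever the date of contact.
3. Reconcile last dose and discontinuation across these passages and 7.7, so that collection never ends before the SAP window. The words at least matter: for a patient stopped after a 21-day interruption, a plain switch to 28 to 35 days after last dose would bring the contact forward from the days 42 to 56 that 6.5.3 literally gives.

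The shortfall then becomes 0 days, and onsets on days 29 to 35 may be collected but fall outside the SAP count, so TEAE counts no longer depend on the call date. The number of contacts is unchanged. The cost is that sites can no longer call early and that both the protocol and the SAP need amended wording.

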5.3.1 Procedures for discontinuation of a patient from investigational product

Patients may be discontinued from investigational product in the following situations:

- Patient decision. The patient is at any time free to withdraw his/her participation in the study, without prejudice.
- Adverse events (see Table 1).
- Initiation of further line(s) of anti-cancer treatment (including bone marrow transplantation).
- Severe non-compliance to this protocol as judged by the investigator and/or Study Team.
- Disease progression as per 2014 Lugano classification, unless, in the opinion of the investigator, the patient is still deriving clinical benefit.
- Patients incorrectly initiated on investigational product (Section 5.3.2).
- Patient achieved a satisfying response confirmed for 1 year by PET or CT assessment (Section 5.1.4).
- Treatment duration reaching 2 years (approximately 35 cycles) (Section 5.1.4).

• Pregnancy.

Once study medication is permanently discontinued it cannot be restarted.

Any patient who discontinues study treatment for reasons other than disease progression should have response assessment performed as scheduled in the protocol until disease progression is documented or death occurs, unless consent is withdrawn. Study procedure related SAEs and anti-cancer treatment must be captured until the patient no longer has response assessments (disease progression or permanent withdrawal from the study).

After the final database lock, there may be some patients remaining on study treatment. For these patients, sponsor will collect information during the treatment period and for 28 days (\pm 7 days) after last dose on SAEs, death (including those due to disease progression), discontinuation due to AEs/SAEs and drug accountability.

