6.5.1 Definition of adverse events

Any untoward medical occurrence in a patient or clinical investigation patient administered a pharmaceutical product and which does not necessarily have to have a causal relationship with this treatment. An adverse event (AE) can therefore be any unfavorable and unintended sign (including an abnormal laboratory finding, for example), symptom, or disease temporally associated with the use of a medicinal product, whether or not considered related to the medicinal product.

Any deterioration of the disease under study and associated symptoms or findings should not be regarded as an adverse event as far as the deterioration can be anticipated.

The term adverse event is used generally to include any AE whether serious or non-serious.

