6.5.4 Reporting of serious adverse events

All SAEs have to be reported, whether or not considered causally related to the investigational product, or to the study procedure(s). SAEs should be reported to Dizal and recorded in CRF according to Section 6.5.3.

If any SAE occurs in the course of the study, then investigators or other site personnel inform appropriate Sponsor representatives immediately, or **no later than 24 hours** of when he or she becomes aware of it.

The designated Sponsor representative works with the investigator to ensure that all the necessary information is provided to appropriate patient safety database within one calendar day of initial receipt for fatal and life-threatening events and within five calendar days of initial receipt for all other SAEs.

For fatal or life-threatening adverse events where important or relevant information is missing, active follow-up is undertaken immediately. Investigators or other site personnel inform Sponsor representatives of any follow-up information on a previously reported SAE immediately, or no later than 24 hours of when he or she becomes aware of it. The SAE will be reported to the designated sponsor representative via the study SAE paper form.

The Sponsor representative will advise the investigator/study site personnel how to proceed.

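### Table 5 omits SAEs unrelated to a procedure before first dose, and its footnote on late SAEs leaves out drug-related events that section 6.5.4 requires to be reported

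*Protocol*

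**What the plan says.** Protocol 6.5.3 sets the recording window in its text: "However, SAE should be collected and recorded in eCRF from ICF signing to the end of defined follow-up period". It attaches no causality limit and points to Table 5 as the summary. Footnote D of the Part A schedule, footnote F of the Part B schedule and footnote F of SAP Appendix A repeat the rule.

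Table 5 has three periods: consent to first dose, first dose to the follow-up visit, and after that visit but before progression. The row "Record all new AEs in CRF" reads No, Yes, No. The row "Record all study procedure related new SAEs in CRF" reads Yes, Yes, No. The three-asterisk footnote on that last No keeps new late SAEs, including deaths, out of the eCRF, "but still need to be reported to Dizal in the condition of causality with study procedure judged by investigator". A separate paragraph of 6.5.3 asks for notification of SAEs possibly related to AZD4205, but only for patients who have completed the study.

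Three other sections bear on the late period:

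- 5.3.1, on patients who stop drug without progression: "Study procedure related SAEs and anti-cancer treatment must be captured until the patient no longer has response assessments".
- 6.9.5.1: after the 28-day visit, only later cancer therapy and response assessments are collected.
- 6.5.4: every SAE must be reported irrespective of causality, and any SAE arising during the study must reach the sponsor within 24 hours. It also says "SAEs should be reported to Dizal and recorded in CRF according to Section 6.5.3".

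**The concern.** A site that works from Table 5 would handle two kinds of event differently from a site that works from the text.

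The first is a screening SAE not caused by a procedure. The second is an SAE attributed to AZD4205 in a patient who is off drug, past the 28-day visit and still on study. The footnote names procedure causality only, and the AZD4205 clause has not yet started.

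The second kind matters more. The protocol treats serious infection as a class risk of JAK inhibitors, reports pneumocystis, zoster and CMV events with AZD4205, and says that new cancers will generally be serious. The Part B stopping criteria in 5.1.2 suspend accrual after a single treatment-related death and state no time window. That rule works only if such deaths are reported.

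**Working it through.** No power, alpha or sample-size figure is involved. The check sets the rules side by side for each period.

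| Period | 6.5.3 text | Table 5 | 6.5.4 | Result |
|---|---|---|---|---|
| Consent to first dose | All SAEs in eCRF | New AEs: No. Procedure-related SAEs: Yes | All SAEs reported | Text and table conflict on eCRF entry |
| First dose to 28 (±7)-day visit | All SAEs in eCRF | New AEs: Yes | All SAEs reported | Agree |
| After that visit, before study completion | eCRF window closed; AZD4205 clause not yet open | Not in eCRF; sponsor report only if procedure-related | All SAEs reported, within 24 hours | Footnote and 6.5.4 conflict on the sponsor report |
| After study completion | Sponsor told if possibly AZD4205-related | Not addressed | Not specific | No conflict on this point |

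**First period.** The one-asterisk footnote rescues only events that begin before dosing and worsen afterwards. A pre-dose SAE unrelated to a procedure that does not worsen has no Yes cell in Table 5.

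**Second period.** Section 6.5.1 settles it: "The term adverse event is used generally to include any AE whether serious or non-serious". The all-AE row therefore captures every new SAE.

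**Third period: who is in it.** Under 3.1.3, Part B patients who stop drug without having progressed are not treated as withdrawn and keep being assessed. Sections 5.1.4 and 5.3.1 create such patients by design, since treatment may end after a satisfying response lasting more than a year, or at two years. Patients stopping for toxicity join them. For a rough scale, 5.1.2 gives 13.9% as the Part A rate of TEAEs leading to discontinuation. If that held in Part B, 0.139 × 100 = 13.9, or about 14 of 100 patients, fewer once early progression and death are removed. Responders who stop as planned come on top, and their number cannot be derived. Nor can the number of late SAEs.

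**Third period: whether another section fills the gap.** Section 5.3.1 names procedure-related SAEs only. Section 6.9.5.1 names no SAEs. Footnote C of the Part B schedule provides for contact after progression on survival, later treatment and unresolved AEs, and does not mention new SAEs. Section 6.5.2, however, defines an SAE as one occurring in any study phase, including follow-up. The deaths text in 6.5.3 makes any on-study death not clearly due to progression reportable as an SAE within 24 hours. The protocol is therefore not silent: the footnote says one thing, and 6.5.4 and the deaths text say another.

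**Effect on the analysis.** The SAP (4.3.2, 5.7.1) confines AE summary tables to TEAEs, which run from first dose to at most 28 days after the last dose. The first period lies before that window. The correction for the third period concerns sponsor reports, not eCRF entries. The TEAE tables therefore stay as they are. SAE listings could gain pre-treatment events, because the SAP lists all individual AE data with a treatment-emergence flag.

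**The case against.** The case against is substantial. Table 5 is only a summary, and four explicit statements across the two documents give the all-SAE rule from consent; one row label is out of step. The duties in 6.5.4 to report every SAE, and to do so within 24 hours, are separate sentences with no causality limit. Deaths have their own text. Ending routine eCRF entry after a fixed safety window is a legitimate choice. Pre-dose events precede any drug exposure, and uneven collection across sites is a prediction, not something the documents show.

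Much of this stands, and it rules out three stronger readings that a reader might take from Table 5:

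- *SAE recording is limited to procedure-related events throughout.* It is not: from first dose to the follow-up visit the all-AE row covers every SAE.
- *Late drug-related SAEs go wholly unreported.* They fall outside the eCRF and outside the footnote's reporting duty, but inside the general duty of 6.5.4.
- *Section 5.3.1 flatly contradicts Table 5.* Capture in 5.3.1 may mean a safety report, which would fit the footnote. The protocol does not say which is meant.

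The objection does not remove the two conflicts. Section 6.5.4 sends the reader back to 6.5.3 for how SAEs are reported and recorded, and there the footnote is the more specific instruction for the late period. A site following it as written would not report a late SAE that it attributed to AZD4205.

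**Conclusion.** The point holds as two internal contradictions. Before first dose, Table 5 conflicts with the 6.5.3 text and the schedule footnotes on eCRF entry of SAEs unrelated to a procedure. Between the 28-day visit and study completion, the three-asterisk footnote conflicts with 6.5.4 and the deaths text on sponsor reporting of SAEs that are not procedure-related, including drug-related ones.

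The exposure is up to 28 days of screening for each patient, and the late interval for patients who remain on study after the 28-day visit. The figure of about 14 patients stopping for toxicity assumes that the Part A rate carries over, and is only a guide to scale. The consequence is for safety oversight, and for the accrual rule while accrual is open. Efficacy results and TEAE summaries are not touched. The conclusion rests on reading a patient under continued assessment as not having completed the study, which 3.1.3 supports.

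**What to change.** 1. Relabel the Table 5 SAE row as all new SAEs, so that the cell for consent to first dose matches the text. The second-period cell then repeats what the all-AE row already gives, and the third can stay No.
2. Extend the reporting duty in the three-asterisk footnote to SAEs judged related to AZD4205 or to a study procedure.
3. Reconcile 6.5.3, 6.5.4, 5.3.1 and 6.9.5.1 for the time after the 28-day visit, and state whether capture in 5.3.1 means the eCRF or the safety database.

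The cost is one row label, one footnote, some cross-references and a few additional SAE reports. No SAP TEAE table changes.
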